Appendix 6: Potentially Clinically Significant Laboratory Criteria

(Local Laboratory Results)

Parameter	SI Unit	Lower Limit	Higher Limit	% Decrease from Bio-safety Level (BSL)	% Increase from BSL
CHEMISTRY					
Blood Urea Nitrogen (BUN)	mmol/L	NA	>1.5 *ULN	NA	>100
Creatinine	mg/dL	NA	>1.5 *ULN	NA	>50
Sodium	mmol/L	<0.85 *LLN	>1.1 *ULN	>10	>10
Potassium	µmol/L	<0.8 *LLN	>1.2 *ULN	>20	>20
Chloride	mmol/L	<0.8 *LLN	>1.2 *ULN	>20	>20
Carbon Dioxide (Bicarbonate)	mmol/L	<0.7 *LLN	>1.3 *ULN	>40	>40
Glucose	mmol/L	<0.6 *LLN	>3.0 *ULN	>40	>200
Total Bilirubin	mg/dL	NA	>2.5 *ULN	NA	>150
Direct Bilirubin	mg/dL	NA	>1.5 *ULN	NA	>150
Alkaline Phosphatase	U/L	<0.5 *LLN	>2.0 *ULN	>80	>100
Aspartate Aminotransferase (AST)	U/L	NA	>3.0 *ULN	NA	>200
Alanine Aminotransferase (ALT)	U/L	NA	>3.0 *ULN	NA	>200
HEMATOLOGY					
Hematocrit	Ratio	<0.8 *LLN	>1.3 *ULN	>20	>30
Hemoglobin	g/L	<0.8 *LLN	>1.3 *ULN	>20	>30
Platelet Count	10 ⁹ /L	<0.65 *LLN	>1.5 *ULN	>50	>100
White Blood Cell Count	10 ⁹ /L	<0.65 *LLN	>1.6 *ULN	>60	>100
Neutrophils, absolute cell count	10 ⁹ /L	<0.65 *LLN	>1.6 *ULN	>75	>100

Parameter	SI Unit	Lower Limit	Higher Limit	% Decrease from Bio-safety Level (BSL)	% Increase from BSL
Lymphocytes, absolute count	10 ⁹ /L	<0.25 *LLN	>1.5 *ULN	>75	>100
Eosinophils, absolute count	10 ⁹ /L	NA	>4.0 *ULN	NA	>300
Monocytes, absolute count	10 ⁹ /L	NA	>4.0 *ULN	NA	>300
Basophils, absolute count	10 ⁹ /L	NA	>4.0 *ULN	NA	>300
COAGULATION					
Partial Thromboplastin Time (aPTT)	sec	<0.5 *LLN	>2.0 *ULN	>100	>100
Prothrombin Time (PT)	sec	<0.5 *LLN	>2.0 *ULN	>100	>100
International Normalized Ratio (INR)	Ratio	<0.5 *LLN	>2.0 *ULN	>100	>100

LLN: Lower limit of normal value provided by the local laboratory

ULN: Upper limit of normal value provided by the local laboratory

NCA	Non-compartmental analysis
NDA	New drug application
PK	Pharmacokinetic
PT	Preferred term
PVA	Polyvinyl alcohol
SAE	Serious adverse event
SD	Standard deviation
SoA	Schedule of Activities
SOC	System organ class
t _{1/2}	Elimination half-life
TEAE	Treatment-emergent adverse event
TID	Thrice daily
t _{max}	Time take to reach Cmax
TNF- α	Tumor necrosis factor-alpha
VSS	Volume of distribution at steady state
WBC	White blood cell
WHO	World Health Organization

1. INTRODUCTION

The purpose of this plan is to prospectively outline in detail the data derivations, statistical methods and presentations of data so that valid conclusions can be reached to address the study objectives outlined in the protocol ANA001-002, dated 22 October 2020.

The planned analyses identified in this statistical analysis plan (SAP) may be included in regulatory submissions and/or future manuscripts. Exploratory analyses, not identified in this SAP, may be performed to support the clinical development program. Any post-hoc or unplanned analyses that are performed but not identified in this SAP will be clearly identified in the clinical study report (CSR).

1.1. Responsibilities

Inference, Inc will perform the statistical analyses for all clinical data collected. Inference, Inc is responsible for production and quality control of all tables, figures and listings.

1.2. Timing of Analyses

Data from the SAD Cohorts S1 through S3 will be summarized and evaluated to determine the doses and schedule to be used in a potential fourth SAD cohort and the MAD BID or TID cohorts. Dosing for the potential fourth SAD Cohort S4 will be based on both safety and PK data.

The final analysis will be performed after all subjects complete the study and the database is locked.

1.3. Interim Analysis

The interim analysis based on data from the SAD Cohorts S1 through S3 will be done using aggregate summaries to preserve blinding. The analysis will include listing of safety data, including adverse events. Serious and drug-related adverse events will be taken into in determining the dosing in the MAD part of the study. It may also involve evaluation of laboratory safety data. These analyses will be based on the Safety Analysis.

For evaluating the pharmacokinetics of single dose ANA001, plots of mean (SD) plasma concentration by time will be presented for ANA001 by cohort/dose in linear and semi-logarithmic scales. Pharmacokinetic parameters will also be calculated by each cohort/dose using the methods describes in Section 8, but will use nominal times instead of actual sampling times.

2. STUDY OBJECTIVES AND ENDPOINTS

2.1. Study Objectives

Primary Objectives:

- To assess safety and tolerability of single oral daily doses of ANA001 (1,000 mg, 2,000 mg and 3,000 mg)
- To assess safety and tolerability of multiple daily oral doses (twice daily [BID] or thrice daily [TID]) of ANA001 for 7 days

Secondary Objectives:

- To assess the PK of single and multiple doses of ANA001

2.2. Endpoints

2.2.1. Primary Outcome Measures

The primary outcome measures are the following safety and tolerability endpoints:

- Incidence of:
 - Treatment-emergent adverse events (AEs)
 - Treatment-emergent serious AEs (SAEs)
 - Study drug discontinuation due to a TEAE (MAD portion only)
- Use of concomitant medications
- Incident of treatment-emergent clinical laboratory tests abnormality
- Change from baseline by visit in:
 - Clinical laboratory tests
 - Vital signs
 - Electrocardiograms (ECG)
 - Physical examinations

2.2.2. Secondary Endpoints

The secondary outcome measures are the following pharmacokinetic endpoints:

- $AUC_{(0-t)}$
- $AUC_{(0-\text{last})}$
- $AUC_{(0-\infty)}$ (SAD only)
- C_{\max}
- t_{\max}

ANA THERAPEUTICS, INC.
Protocol ANA-001-002
STATISTICAL ANALYSIS PLAN

- $t_{1/2}$
- CL/F
- Vz/F

3. STUDY DESIGN

This is a randomized, double blind study to be conducted in two parts: single ascending dose (SAD) and multiple ascending dose (MAD).

SAD

Eligible participants will be randomly assigned to active drug (ANA001) or placebo in an 8:2 ratio. On Day 1, following an overnight fast of at least 10 hours, participants will receive their assigned treatment (1000 mg, 2000 mg, or 3000 mg of ANA001) with a standardized light meal.

A baseline ECG will be performed at Screening and at 3 hours post-dose. Blood pressure and heart rate will be measured every 8 hours while confined to the clinic. Blood for PK will be collected pre-dose and at 0.5, 1, 2, 4, 6, 8, 10, 12, and 24 hours post-dose. Participants will be discharged on Day 2 following the 24-hour PK sample and completion of clinical laboratory tests and physical examination. They will return on Day 7 (± 2) for follow-up procedures including physical examination, laboratory tests, and assessment of AEs and concomitant medication use.

SAD study design:

Cohort S1: 1000 mg (n=8) or placebo (n=2), single dose
Cohort S2: 2000 mg (n=8) or placebo (n=2), single dose
Cohort S3: 3000 mg (n=8) or placebo (n=2), single dose
Cohort S4: xx mg (n=8) or placebo (n=2) (optional; to be determined)

MAD

Eligible participants will be randomly assigned to active drug (ANA001) or placebo in a 10:2 ratio on a BID (q12h) or TID (q8h) schedule, to be determined based on the PK results of the SAD cohorts. Total daily doses are anticipated to range between 2000 mg and 4500 mg of ANA001. On Days 1 through 7, participants will receive their assigned treatment in the morning with a standardized light meal following an overnight fast of at least 10 hours. Afternoon or evening doses will be given with a light snack. A baseline ECG will be performed at Screening and at 3 hours after the second dose on Day 7. Blood pressure and heart rate will be measured every 8 hours while confined to the clinic.

During BID dosing, blood for PK will be collected on Days 1 and 7 at pre-dose and at 0.5, 1, 2, 4, 6, 8, 10, and 12 hours post-dose. Blood samples will also be collected on Days 2, 4, 6, and 8 at pre-dose and before the 12 hour dose on Days 2, 4, and 6.

During TID dosing, blood for PK will be collected on Days 1 and 7 at pre-dose and at 0.5, 1, 2, 4, 6, and 8 hours post-dose. Blood samples will also be collected on Days 2, 4, 6, and 8 at pre-dose, before the 8 hour dose on Days 2, 4, and 6, and before the 16 hour dose on Day 6.

Participants will be discharged on Day 8 following the last PK sample and completion of clinical laboratory tests and physical examination. They will return on Day 15 (± 2) for follow-up

procedures including physical examination, laboratory tests, and assessment of AEs and concomitant medication use.

MAD study design:

Cohort M1: xx mg (n=9) or placebo (n=3) BID or TID for 7 days

Cohort M2: xx mg (n=9) or placebo (n=3) BID or TID for 7 days

Cohort M3: xx mg (n=9) or placebo (n=3) BID or TID for 7 days

3.1. Sample Size Justification

Sample size was not based on statistical considerations. A minimum of 30 participants will be enrolled in the SAD part and up to 36 participants in the MAD part. At least 3 participants of each sex will be included in each cohort.

3.2. Schedule of Activities (SoA)

The following assessments will be performed in this study:

Table 1 Schedule of Activities for SAD

	Screening	In-Patient		Discharge	Follow-up
Study Day	-30 to -2	-1	1	2	7±2
Study PROCEDURES					
COVID PreScreen informed consent	X				
Full study informed consent	X				
Medical history	X				
Prior medications	X				
Physical examination	X				
Abbreviated PE		X	X	X	X
Viral Serology (HIV, HCV, HBV)	X				
Urine alcohol and drug screen	X	X			
Inclusion / exclusion criteria	X	X			
Pregnancy test for WOCBP	X	X			
Randomization		X			
CPU Admission & Confinement		X	X		
CPU Discharge				X	
Drug Administration ^a			X		
Vital signs ^b	X	X	X	X	X
Height	X				
Weight	X	X			
ECG ^c	X		X		
Hematology	X	X		X	X

	Screening	In-Patient		Discharge	Follow-up
Study Day	-30 to -2	-1	1	2	7±2
Study PROCEDURES					
Serum chemistry	X	X		X	X
Urinalysis	X			X	X
Pharmacokinetics ^d			X	X	
Adverse events			Continuous		
Concomitant medications			Continuous		

WOCBP = woman of child-bearing potential

a.) Administered with Standardized light meal

b.) Blood pressure and heart rate supine for 3 to 5 mins and every 8 hours during CPU confinement

c.) Supine for 5 mins at Screening and 3 hours postdose

d.) 4 mL Predose and 0.5, 1, 2, 4, 6, 8, 10, 12 and 24 hr post dose

Table 2 Schedule of Activities for MAD

Study Day	Screening	Confinement/Treatment Period								Discharge	Follow-up
	-30 to -2	-1	1	2	3	4	5	6	7	8	D15±2
Study PROCEDURES											
COVID PreScreen ICF	X										
Full study informed consent	X										
Medical history	X										
Prior medications	X										
Physical examination	X										
Abbreviated PE		X		X			X			X	X
Viral Serology (HIV, HCV, HRV)	X										
Study Day	Screening	Confinement/Treatment Period								Discharge	Follow-up
	-30 to -2	-1	1	2	3	4	5	6	7	8	D15±2
Study PROCEDURES											
COVID Surveillance (ELISA)		+ Swab			X			X			
Urine alcohol and drug screen	X	X									
Pregnancy test for WOCBP	X	X									
Inclusion / exclusion criteria	X	X									
Randomization		X									
CPU Admission & Confinement		X	X	X	X	X	X	X	X		
CPU Discharge											X
Drug Administration ^a			X	X	X	X	X	X	X		
Vital signs ^b	X	X	X	X	X	X	X	X	X	X	X
Height	X										
Weight	X										
ECG ^c	X								X		
Hematology	X	X		X			X			X	X
Serum chemistry	X	X		X			X			X	X
Urinalysis	X			X			X			X	X
Pharmacokinetics ^d			X	X	X	X	X	X	X	X	
Adverse events										Continuous	
Concomitant medications										Continuous	

WOCBP = woman of child-bearing potential

a.) Administered with standardized light meal (500 to 750 cal) in AM and light snack (PM) if BID (q12h) or TID (q8h) daily on days 1 through 6 and a single AM dose on day 7

b.) Blood pressure and heart rate supine for 3 to 5 mins and every 8 hours during confinement

c.) Supine for 5 mins at Screening and at 3 hours after second dose on Day 7

d.) see Table 3

Table 3 Schedule of PK Sampling for MAD

Time (hr)	PK Sampling (4 mL) Study Day BID Dosing							
	1	2	3	4	5	6	7	8
PreDose	X ^a	X ^a		X ^a		X ^a	X ^a	X ^a
0.5	X						X	
1	X						X	
2	X						X	
4	X						X	
6	X						X	
8	X						X	
10	X						X	
12	X	X ^a		X ^a		X ^a	X ^a	
PK Sampling (4 mL) Study Day TID Dosing								
Time (hr)	1	2	3	4	5	6	7	8
PreDose	X ^a	X ^a		X ^a		X ^a	X ^a	X ^a
0.5	X						X	
1	X						X	
2	X						X	
4	X						X	
6	X						X	
8	X	X ^a		X ^a		X ^a	X ^a	

^a Predose

4. ANALYSIS SETS

Screened participants will be defined as any participant who has signed the ICF. Screened participants who meet all eligibility criteria will be considered enrolled into the study and eligible to receive the single dose of ANA001.

There will be two analysis populations in this study:

Analysis Population	Description
Enrolled	All participants who sign the ICF
Safety Population	All participants randomly assigned to study treatment and who take at any amount of study treatment. Participants will be analyzed according to the treatment they actually received.
Pharmacokinetic (PK) Population	All participants randomly assigned to study treatment, who take at least 1 dose of study treatment, and contribute at least 1 post-dose evaluable PK sample. Participants will be analyzed according to the dose they actually received.

5. GENERAL ASPECTS OF THE STATISTICAL ANALYSIS

5.1. Analysis of the Two Parts

The analyses for the SAD and MAD parts will be presented separately.

5.2. Key Definitions

The Study Day is the day relative to the day of study drug administration (Day 1).

Unless otherwise specified, Baseline is the last non-missing observation before the administration of study drug. The treatment period in both the SAD and MAD parts of the study is defined as Days 1-7 for subjects dosed with study drug.

5.3. Visit Windows and Time Points

There are no plans to derive visit windows, and visits will be used in the analyses as reported on the eCRF.

5.4. Multiplicity Issues

For this early phase study, no multiplicity adjustment will be necessary as no comparisons are being made.

5.5. Subgroup Analyses

Due to the small size of this study, no subgroup analyses are planned.

5.6. Missing Data

For prior and concomitant medication summaries, if the medication start date is completely missing then the medication will be considered both prior *and* concomitant unless it can be determined that the medication end date occurred prior to the study drug administration. If the medication start date is partially missing and the partial date is not sufficient to determine if the medication was taken after study drug administration then the medication will be considered both prior *and* concomitant for the study unless the partial date is clearly after the date of study drug administration (in which case it will be considered concomitant only) or the medication end date is prior to study drug administration (in which case it is prior only).

Completely missing or partially missing adverse event onset dates will be imputed as follows in case due diligence to obtain accurate adverse event information fails:

- If the adverse event start date is completely missing then the adverse event will be considered treatment emergent unless it can be determined that the adverse event end date

occurred prior to administration of study drug. If this is the case, the adverse event will not be considered treatment emergent.

- If the adverse event start date is partially missing and the partial date is not sufficient to determine if the event occurred after the administration of study drug, then the adverse event will be considered treatment emergent unless it can be determined that the adverse event end date occurred prior to the start of the study.

Imputation of missing PK data are detailed in the PK section (section 8.1).

No other missing data will be imputed.

6. DEMOGRAPHIC AND BASELINE CHARACTERISTICS

6.1. Subject Disposition and Populations

Summary tables for subject disposition will be presented for all enrolled subjects, by cohort/dose and overall. The subject disposition summary will contain the numbers of subjects who signed informed consent, failed screening, were randomized, completed the study, and discontinued during the study.

The primary reasons for premature discontinuation during the treatment period will be summarized for the Safety Population.

Number of subjects included in each analysis population will also be displayed.

Listings will be presented on subject disposition and protocol violations.

6.2. Demographic and Baseline Characteristics

All subjects in the Safety Population will be used to summarize the demographic and baseline characteristics with respect to key variables such as age, sex, race, height, weight, and BMI by cohort/dose and overall. Summaries for other variables may be provided if needed.

Continuous variables will be summarized with descriptive statistics: n, mean, standard deviation, median, minimum and maximum value. Categorical variables will be summarized with the number and percentages for each cohort.

Demographic and baseline characteristics such as COVID-19 screening, pregnancy test for WOCBP, urine alcohol and drug, and serology (HIV, HBV, HCV) tests will be listed for each subject.

6.3. Medical History

Medical history including existing diseases will be coded according to the latest version of the MedDRA dictionary. Incidence tables of the number and percentage of subjects by system organ class (SOC) and preferred term (PT) by cohort/dose and overall will be provided for the Safety Population.

Medical history will also be listed by subject.

6.4. Prior and Concomitant Medication

Medications will be separated into prior and concomitant medications. Prior medications are those with start and stop date before the date of study drug administration. Concomitant medications are those with either start date prior to the date of study drug administration and were ongoing while

for the duration of the study *or* those with start date after the date of study drug administration. A medication can be considered both prior and concomitant.

All medications will be coded according to the latest version of the WHO Drug Dictionary and listed by subject. Prior and concomitant medications will be flagged accordingly.

7. PHARMACOKINETIC ANALYSIS

For PK analysis of ANA001, blood samples will be collected during the entire treatment period according to the PK sampling schedules in the SoA. All PK analysis will be based on the PK Population.

7.1. Handling Missing or Non-Quantifiable Data

Below Limit of Quantitation (BLQ) values will be set to zero prior to calculation of descriptive statistics for the plasma concentration-time profile and the log-concentration value will be set to 0 if the value is used in calculating geometric means. Actual elapsed time from dosing will be used to estimate all individual plasma pharmacokinetic parameters. Any anomalous concentration values observed at the pre-dose time point within a period will be examined for the understanding of such an occurrence, and subsequently will result in the exclusion of the subject from the primary AUC analysis, or be assigned a numerical zero for calculating AUC and identified in the CSR.

BLQ value(s) that occur at the beginning of serial sampling (before the first quantifiable concentration value) will be treated as zero, and BLQ value(s) that occur at the end of serial sampling (that is, after the last quantifiable concentration value) will be treated as missing. A BLQ value that is embedded between two quantifiable points will be treated as missing data. If consecutive BLQ concentrations are followed by quantifiable concentrations in the terminal portion of the concentration curve, these quantifiable values will be excluded from the pharmacokinetic analysis by assigning them a value of missing unless otherwise warranted by the concentration-time profile.

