A minimum of 30 participants will be enrolled in the SAD part and up to 36 participants in the MAD part. At least 3 participants of each sex will be included in each cohort.

Treatment Groups and Duration:

SAD

Cohort S1: 1000 mg (n=8) or placebo (n=2), single dose

Cohort S2: 2000 mg (n=8) or placebo (n=2), single dose

Cohort S3: 3000 mg (n=8) or placebo (n=2), single dose

MAD

Cohort M1: xx mg (n=9) or placebo (n=3) BID or TID for 7 days

Cohort M2: xx mg (n=9) or placebo (n=3) BID or TID for 7 days

Cohort M3: xx mg (n=9) or placebo (n=3) BID or TID for 7 days

Investigational Product, Dose, and Mode of Administration

ANA001 capsule containing 250 mg niclosamide, administered orally as 4, 6, 8 or 12 capsules with a light meal (500 to 750 cal) or snack.

Statistical Methods

Sample Size Determination:

Sample size was not based on statistical considerations.

Safety Analysis:

All participants who received at least one dose of study drug will be included in the safety analysis. Safety will be assessed by the incidence and frequency of AEs, and changes in physical examinations, vital signs, clinical laboratory tests, and ECGs. Results will be summarized using descriptive statistics (mean, standard deviation [SD], coefficient of variation [%CV], median, minimum, maximum).

Pharmacokinetic Analysis:

All participants on active treatment who contributed at least one post dose blood sample, evaluable for drug PK concentration will be included in the PK analysis. PK parameters, calculated using non-compartmental models, include $AUC_{0-\infty}$, AUC_{0-t} , $AUC_{0\text{-last}}$, C_{max} , t_{max} , $t_{1/2}$, CL/F , and V_z/F . Results will be summarized using descriptive statistics (mean, standard deviation [SD], coefficient of variation [%CV], median, minimum, maximum). Plasma concentration-time profiles will be plotted.

2. Schedule of Activities (SoA)

Table 1 Schedule of Activities for SAD

	Screening	In-Patient		Discharge	Follow-up
Study Day	-30 to -2	-1	1	2	7±2
Study Procedures					
COVID Pre-screen informed consent	X				
Full study informed consent	X				
Medical history	X				
Prior medications	X				
Physical examination	X				
Abbreviated PE		X	X	X	X
Viral Serology (HIV, HCV, HBV)	X				
Urine alcohol and drug screen	X	X			
Inclusion / exclusion criteria	X	X			
Pregnancy test for WOCBP	X	X			
Randomization		X			
CPU Admission & Confinement		X	X		
CPU Discharge				X	
Drug Administration ^a				X	
Vital signs ^b	X	X	X	X	X
Height	X				
Weight	X	X			

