7.2. Pharmacokinetic Concentration Analysis

Plasma concentrations of ANA001 will be summarized by cohort/dose and nominal timepoint with descriptive statistics: n, mean, SD, CV%, geometric mean, geometric CV%, median, minimum, and maximum.

Linear and semi-logarithmic plots of the mean plasma concentration by actual sampling time will be provided by cohort. For the MAD part, these plots will be done for both Day 1 and Day 7. Individual subject plots may also be provided for ANA001 in linear and semi-logarithmic plasma concentrations. Additionally, for the MAD part, plots of the trough concentrations by dosing intervals may be plotted to understand the achievement of steady state.

For each part, plasma concentrations of ANA001 at each nominal timepoint will be listed by subject.

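### SAP 7.1 gives BLQ concentrations a log value of 0, so geometric means in the concentration tables take each BLQ value as 1 reporting unit and depend on the unit

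*SAP*

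**What the plan says.** The opening sentence of SAP 7.1 holds two rules for the same BLQ observation. For the concentration-time profile, "Below Limit of Quantitation (BLQ) values will be set to zero prior to calculation of descriptive statistics". For geometric means, "the log-concentration value will be set to 0 if the value is used in calculating geometric means". The second rule is conditional, and the SAP does not say when a BLQ value is used.

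SAP 7.2 puts geometric statistics into the concentration tables, which are "summarized by cohort/dose and nominal timepoint with descriptive statistics: n, mean, SD, CV%, geometric mean, geometric CV" (in %), followed by median, minimum and maximum.

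The second paragraph of 7.1 works by position in the profile. Leading BLQ values count as zero, embedded ones are missing, and "BLQ value(s) that occur at the end of serial sampling (that is, after the last quantifiable concentration value) will be treated as missing".

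The supplied SAP text gives no reporting unit and no LLOQ. SAP 11 places table layouts in a separate Data Displays Document. The geometric columns are an addition by the SAP. The Protocol synopsis says of the PK analysis: "Results will be summarized using descriptive statistics (mean, standard deviation [SD], coefficient of variation [%CV], median, minimum, maximum".

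**The concern.** A geometric mean should describe the same concentration whatever unit it is computed in. Here it does not, because the substituted value is fixed on the log scale and not as a concentration. One BLQ sample becomes 1 ng/mL in one unit and 1 µM (327.1 ng/mL) in another. In the larger unit the substituted value can exceed the quantifiable results, so a BLQ sample raises the geometric mean.

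Rows with BLQ values will occur. Both parts sample before the first dose, when drug-naive subjects should be BLQ. Taken literally, the rule gives that row a geometric mean of 1 beside a mean, median, minimum and maximum of 0, which no real data can produce.

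The stake is limited. The rule concerns summaries of concentration. The secondary endpoints are different quantities: "The secondary outcome measures are the following pharmacokinetic endpoints", namely AUC, Cmax, tmax, half-life, CL/F and Vz/F. The accumulation ratios and the power model use those parameters. The figures use arithmetic means: at the interim, "plots of mean (SD) plasma concentration by time will be presented", and at the end, "Linear and semi-logarithmic plots of the mean plasma concentration by actual sampling time will be provided by cohort". Safety is not involved.

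**Working it through.** The plan states no figure for this point, so there is nothing to reproduce. The check is direct algebra with illustrations.

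**Inputs from the documents.** Molecular weight 327.1 g/mol (Protocol 3.2.1), so 1 µM = 327.1 ng/mL. Active n per SAD cohort is 8 (SAP 3). For MAD, SAP 3 gives both 9 (cohort list) and 10 (10:2 ratio), so both are shown. Protocol 3 quotes literature concentrations in both units, for example 249 ng/mL = 0.76 µM. It does not say which unit this study will report.

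**Assumptions.** The number of BLQ values k, the LLOQ, and the geometric mean g of the quantifiable values. The documents give none of these.

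**Step 1: geometric mean under the rule.** With k of n values at log 0, GM = exp[((n−k)/n)·ln g] = g^((n−k)/n), with g in the reporting unit. After conversion back to one unit, the µM result divided by the ng/mL result is 327.1^(k/n), whatever g and the LLOQ are.

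| n | k=1 | k=2 | k=3 |
|---|---|---|---|
| 8 | 2.06 | 4.25 | 8.77 |
| 9 | 1.90 | 3.62 | 6.89 |
| 10 | 1.78 | 3.18 | 5.68 |

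Example with n=8 and every quantifiable value at 249 ng/mL:
- One BLQ: 124.9 ng/mL if computed in ng/mL, 257.6 ng/mL if computed in µM.
- Two BLQ: 62.7 and 266.6 ng/mL.

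Both µM results exceed 249, the only concentration actually measured.

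**Step 2: departure from LLOQ/2 within one unit.** The ratio of the rule to LLOQ/2 is (2/LLOQ)^(k/n) in ng/mL and (654.2/LLOQ)^(k/n) in µM, with LLOQ in ng/mL and 654.2 = 2 × 327.1. For 2 of 8 BLQ:

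| Assumed LLOQ (ng/mL) | 1 | 2 | 5 | 10 |
|---|---|---|---|---|
| Reported in ng/mL | 1.19 | 1.00 | 0.80 | 0.67 |
| Reported in µM | 5.06 | 4.25 | 3.38 | 2.84 |

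**Step 3: geometric CV, if it uses the same logs.** That is the natural reading, but the SAP names only geometric means. Geometric CV = √(exp(s²)−1). If the quantifiable logs have sample variance ln 1.25 (geometric CV 50%, assumed), then for n=8 and k=2, s² = [5·ln 1.25 + 1.5·(ln g)²]/7.
- g = 5 ng/mL: 102% in ng/mL, 697% in µM.
- g = 20 ng/mL: 265% and 229%.
- g = 100 ng/mL: 1046% and 76%.

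The order reverses at g = √327.1 = 18.1 ng/mL.

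**Step 4: which paragraph of 7.1 governs the tables.** The two readings are alternatives. Take 2 trailing BLQ values of 8, in ng/mL. Paragraph 1 gives g^(6/8) with n=8; paragraph 2 gives g with n=6.
- g = 5: 3.3 against 5.0 (1.50-fold).
- g = 20: 9.5 against 20.0 (2.11-fold).
- g = 100: 31.6 against 100 (3.16-fold).

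The arithmetic mean differs by 8/6 = 1.33. If paragraph 2 does govern the tables, trailing and embedded BLQ values drop out and the log rule applies only to leading ones.

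**The case against.** The strongest reply is that a study reports in one unit. The cross-unit ratios then compare two tables of which only one will exist. If the unit is ng/mL, step 2 shows a modest departure from a conventional substitution, and none at an LLOQ of 2 ng/mL. The large figures need µM reporting, which nothing in the documents promises. This stands as a limit on size. It does not rescue the rule, because agreement with LLOQ/2 at one particular LLOQ is a coincidence and the all-BLQ row is wrong in any unit.

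The Data Displays Document may already give the unit, the LLOQ and a display for all-BLQ rows. That is possible, but stating the unit would still not tie the substituted value to the assay.

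The second paragraph of 7.1 reads most naturally as a rule for parameter calculation. It speaks of serial sampling and ends with exclusion from the PK analysis, and isolated MAD troughs are not serial profiles. I agree that this is the likely intent, and the fix only asks for it to be written down. On that reading, every BLQ value in the tables falls under the log rule.

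The geometric CV figures are illustrations resting on several assumptions, as stated. It is also true that no numeric substitution can match the zero used for the arithmetic mean, since log 0 is undefined. The objection to 1 unit is therefore not that it differs from zero, but that it is not a fixed concentration.

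Finally, the anomaly in an all-BLQ row would be visible, and individual concentrations are listed by subject, so a reader could recompute.

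**Conclusion.** The concern holds, as a minor point. Followed literally, SAP 7.1 imputes 1 reporting unit for each BLQ value in a geometric mean. The result depends on the unit whenever k > 0, by 327.1^(k/n) between µM and ng/mL. That algebra needs no assumption beyond the molecular weight. How far the printed values depart from a sensible convention depends on the unit, the LLOQ and the BLQ frequency, none of which the supplied text gives: 0.67 to 1.19 times LLOQ/2 in ng/mL, and 2.84 to 5.06 times in µM, for 2 of 8 BLQ and an LLOQ of 1 to 10 ng/mL. The effect is confined to the geometric columns of the descriptive concentration tables. It does not reach Cmax, AUC, the accumulation ratios, the power model, the arithmetic mean plots or safety.

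**What to change.** 1. Delete the rule that sets the log-concentration to 0.
2. State one unit-invariant convention for the geometric mean and geometric CV of concentrations. Examples are LLOQ/2, or not calculated when BLQ values are present or exceed a stated fraction. The choice and any cut-off are the sponsor's.
3. For rows that are entirely BLQ, print the geometric statistics as not calculated, and show the number of BLQ values.
4. State that the first paragraph of 7.1 governs concentration summaries and the second governs PK parameter calculation only.
5. Footnote the unit, the LLOQ and the use of zero for arithmetic means, unless the Data Displays Document already does so.

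The cost is two or three SAP sentences, one table footnote and trivial programming, with no change to data collection. There is a drawback: some geometric cells may be blank, and the two means will follow different BLQ conventions. Under LLOQ/2 the geometric mean can still exceed the arithmetic one. With 2 of 8 BLQ and the rest at the LLOQ, the geometric mean is 0.5^(2/8) = 0.84 LLOQ and the arithmetic mean is 6/8 = 0.75 LLOQ. The footnote should make that clear.
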